Note: every effort will be made to recruit a diverse group of parent mentors (e.g., parents of children with various subtypes of JIA, parents who live in rural vs urban settings, various ethnicities).

Mentee Criteria.***Inclusion Criteria:***

- (a) English-speaking caregiver of a child diagnosed with JIA according to ILAR criteria (11) prior to their 18th birthday
- (b) access to computer capable of using free Skype software. *Note:* 85% of Canadian households have high speed Internet availability as of 2010 (12).

Exclusion Criteria:

- (a) Significant cognitive impairment or major co-morbid illness of parent that impedes ability to engage in program (e.g., psychosis, active suicidal ideation, cognitive delays that would impact ability to participate and complete questionnaires)

Study Design:

A waitlist pilot RCT design using central randomization with repeated measures will be used to evaluate the feasibility of the iParent2Parent Program. Up to 12 peer mentors will be enrolled across two large tertiary pediatric rheumatology centres (SickKids and IWK Health Centre). A total of 40 consenting parents of children diagnosed with JIA will also be enrolled from two large tertiary pediatric rheumatology centres (SickKids and IWK Health Centre) and randomized to the experimental (iParent2Parent Program) (n=20) or control (waitlist) (n=20) group. The decision was made not to recruit at BC Children's Hospital in order to prevent contamination of the sample given the pilot CF-PSP is currently being evaluated in the rheumatology clinic. BC Children's will be recruiting in the future RCT.

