Parent Mentor Training. Parent mentor training will involve a stepwise approach including both self-directed in-home training and one full day of in-class training facilitated by a psychologist [name] and social worker [name]. In-class training will comprise of lectures, active group discussions, small group activities, and role-play activities. iParent2Parent call topics will be decided by the mentor and mentee. However, the training manual will include suggested topics,

advice on structuring conversations, and guides to redirect conversations. Based on the evidence on parent outcomes (6-8), training will emphasize active listening, fostering adaptive coping, and problem-solving skills. Peer mentors will have access to research staff for additional training and support throughout the duration of the study if needed. This includes consultations with research staff and additional training in mentorship skills.

The following study safeguards will be put in place and any adverse events will be tracked:

- Peer mentor training on confidentiality, boundaries, self-care, and when to seek support.
- Peer mentors will be assigned a study specific online account and email address to encourage appropriate boundaries between mentor and mentee.
- Peer mentor training on emergency identification and reporting using a standardized concerns checklist, appropriate services (e.g., 911), and/or the study or local health care team.
- A member of the research team will contact peer mentors at least bi-monthly to ensure mentors are comfortable in their role, not experiencing any undue stress, and to discuss any concerns with the program.
- [name] will be available to facilitate appropriate referrals as necessary via social work department at SickKids and IWK Health Centre.

Control Group. The control group will be on a waitlist and receive usual care without intervention. The iParent2Parent Program will be offered after completion of all outcome measures.

Both Groups. Primary and secondary outcome measures will be collected online from both groups at baseline, 3 months, and 6 months.

Peer Mentors. Prior to mentor training, mentors will complete baseline outcome measures. Immediately following training, mentors will complete training evaluations. At study end, mentors will complete follow-up outcome measures and participate in a focus group.

Procedure:

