Following ethics approval, eligible parents will be invited to take part in this study by the clinical care team in the rheumatology clinics at SickKids and IWK Health Centre. Participants may also self-identify to the research team by responding to the study posters or postcards that are in the clinics. A site-specific clinical research project coordinator (CRPC) will obtain consent from interested parents. A member of the research team will track the number of eligible parents approached and if voluntarily provided, reasons for refusal. Subsites will be responsible for consenting mentee participants locally. Once informed consent is obtained, the subsite RA will send mentee contact information to SickKids via secure file transfer. A master database of all participants will be housed at SickKids as we are the central hub and primary point of contact for recruitment and study activity.

Once consent is obtained, baseline demographic and disease-related data will be collected from the child's medical charts and pre-intervention measures will be administered online to parent participants. Online measures for this study will be obtained using REDCap (Research Electronic Data Capture) and housed on a secure server.

Randomization: The CRPC will enter participant ID and stratification variables (i.e., disease activity and study centre) for group allocation into a secure, web-based randomization software (Randomizer). Participants will be randomized 1:1 into one of two groups (iParent2Parent or waitlist), and allocation will remain hidden. The CRPC will then contact participants to inform them of group assignment and instruct them on procedures to be followed.

Proposed Methods for Protecting against Sources of Bias

Blinding. The randomization process will be blinded to site-specific staff and co-investigators to reduce the chance of experimenter bias. Mentors and mentees will be asked not to discuss their study involvement with others until study completion. Mentors and mentees will complete all outcome measures online.

Contamination. To minimize the small potential risk of contamination, participants will be asked about their involvement in other peer support groups, other peer mentors, or any other concomitant interventions.

Outcomes Measures:

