- **Primary Outcome:** trial feasibility and acceptability of the iParent2Parent Program. Criteria for feasibility are based on studies previously conducted by our group and will be: accrual rate of >70%, attrition rate of <15%, technical difficulties reported by <10% of parents and mentors, adherence rate of >80%, <5% missed responses on outcome measures and high acceptability (based on qualitative analyses). Data related to the primary outcome will be recorded on investigator-developed forms. Acceptability data will be collected using semi-structured interviews with mentors and mentees at end-of-study.
- **Secondary Outcome:** determination of treatment effect estimates for mentee participants. Effect sizes will be determined for the following: QOL (PROMIS Adult Profile 25 (13), perceived social support (Short form versions of the PROMIS battery for: Social Isolation; Informational Support; and Emotional Support) (13), coping (Coping Health Inventory for Parents (CHIP)(14); and parenting stress (Parental Stress Scale (PSS) (15).
- **Exploratory Outcome:** determination of impact for peer mentors. Effect sizes will be determined for the following: QOL (PROMIS Adult Profile 25) (13), perceived social support (PROMIS Social Isolation; Informational Support; Emotional Support) (13), coping (CHIP) (14), and parenting stress (PSS) (15). Peer mentor perceived benefits and challenges will be collected qualitatively using semi-structured interviews with mentors at end-of-study. Both groups will be asked about additional peer support sought during these time periods.

Statistical Plan:

Feasibility. This project builds on previous and ongoing research conducted by the research team. Our multidisciplinary team comprises of an experienced group of investigators with extensive and collective depth of clinical and research expertise in JIA, parenting chronically ill children, eHealth, QOL, peer support, knowledge translation, qualitative analysis, and mixed methods research.

Sample Size and Recruitment. A total of 20 participants per group is suggested for recruitment in pilot studies to examine intervention feasibility (16). SickKids and IWK Health Centre see over 150 new pediatric JIA diagnoses per year. Using a conservative estimate of 75 children diagnosed in 6 months, with a 30% refusal rate (based on our previous work (17)), we will recruit 40 parents within the timeframe.

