Quantitative data will be analyzed using SAS 9.1.3. Baseline sample characteristics will be summarized. Rates of accrual, attrition, adherence, and missing data with 95% confidence intervals will be calculated. To inform sample size calculations for a larger trial, data will be analyzed as a larger trial and estimates of variance and correlation on secondary and exploratory outcome variables will be estimated. If assumptions for parametric statistics are met, linear mixed models will be used to test intervention effects on all outcomes. We will adjust for important factors such as child age, sex, and number of mentoring sessions in our model. Covariance structure will be selected based on model diagnostic statistics. We will examine patterns of missing data, determine demographic and/or clinical characteristics that are related

to missing data at each time point, and the potential impact on the primary findings. The semi-structured mentor and mentee interviews will be audio-recorded and transcribed verbatim. All transcripts will be verified against recordings and imported into NVivo10. Data will be analyzed using an inductive qualitative content analysis approach (18, 19) and used to refine the intervention before a large-scale RCT. This analytic approach was used in previous RCTs and our research team has the required expertise in qualitative analysis (20, 21).

Impact

Expected Results:

This proposal directly impacts an under-researched area of psychosocial and familial health outcomes in pediatric rheumatology. It will result in the development of a new online peer mentoring program for parents of children with JIA. The results of this pilot study will be leveraged in two significant ways: 1) to apply for a large-scale multi-site grant investigating effectiveness and implementation outcomes of the iParent2Parent Program across Canada; and 2) the iParent2Parent Program will be made adaptable to other childhood rheumatic diseases.

Project Deliverables:

This proposal builds from a strong foundation of collaborations and previous experience developing peer mentorship programs for adolescents with JIA (see Preliminary Work section). This project capitalizes on existing research and clinical knowledge to develop a structured program and manual that other pediatric centres can adopt. The iParent2Parent manual will be created as a standalone resource for selection and training peer mentors as well as how to structure the iParent2Parent Program.

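### The covariates named for the mixed model include neither stratification factor, and the role of the baseline score is left open

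*Protocol*

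**What the plan says.** Under Randomization, the protocol states: "The CRPC will enter participant ID and stratification variables (i.e., disease activity and study centre) for group allocation". It continues: "Participants will be randomized 1:1 into one of two groups (iParent2Parent or waitlist), and allocation will remain hidden". The number of disease-activity levels is not given. There are two centres.

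The Statistical Plan gives the model for the effect estimates: "If assumptions for parametric statistics are met, linear mixed models will be used to test intervention effects on all outcomes". Its only statement on covariates is: "We will adjust for important factors such as child age, sex, and number of mentoring sessions in our model". Neither stratification factor appears there.

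On baseline, the Both Groups paragraph states: "Primary and secondary outcome measures will be collected online from both groups at baseline, 3 months, and 6 months". Study Design describes "A waitlist pilot RCT design using central randomization with repeated measures". The Statistical Plan adds that the covariance structure will be chosen from model diagnostics. Nothing says whether the baseline score is a covariate, one of the repeated responses, or not used in the treatment comparison.

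Both Specific Aims and the Statistical Plan say that the variance estimates from this pilot are meant to size a later, larger trial.

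**The concern.** Two factors were judged important enough to stratify on, yet neither is among the protocol's own examples of important factors for adjustment. An analyst who follows the text has no instruction to include them.

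Stratified allocation balances the arms on these factors. A model that leaves them out does not credit that balance: their contribution stays in the residual variance, and the reported standard error is too large whenever they predict the outcome.

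The role of the baseline score is a separate question with a different consequence. A prognostic baseline that goes unused, or is used inefficiently, costs real precision, and there are only 20 parents per arm.

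The residual variance is itself an intended product of the pilot. If it is inflated and the later trial's analysis does adjust, the calculated sample size rises in the same proportion.

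**Working it through.** **The plan's own figures.** The protocol gives 20 per arm, 40 in total, from a cited rule for pilot studies. It states no alpha, power, SD or effect size, so there is no standard error or variance to reproduce. Its recruitment statement does support 40: 75 × (1 − 0.30) = 52.5.

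**Inputs from the protocol.** 1:1 allocation; 20 per arm; two stratification factors, one of them centre with 2 levels; visits at baseline, 3 and 6 months; a linear mixed model.

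**Assumptions not in the protocol.** Two disease-activity levels, hence 2 × 2 = 4 strata averaging 40/4 = 10 parents; even splits; permuted blocks of 4; outcome SD 1; share of variance explained by the strata (R²) from 0 to 0.3; correlation between visits (ρ) from 0.3 to 0.7.

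**Step 1: strata left out.** The large-sample inflation of the reported standard error is 1/√(1 − R²), which is 1.054 at R² = 0.1 and 1.118 at R² = 0.2. The inflation of residual variance is 1/(1 − R²): 1/0.9 = 1.11, 1/0.8 = 1.25, 1/0.7 = 1.43.

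Simulation at n = 40 compared least-squares models with and without strata main effects. Each row averages three sets of 8,000 trials; the true SE is the spread of the estimates.

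| R² | Reported SE, strata out | True SE, strata out | Ratio | Type I error, strata out | Reported SE, strata in | True SE, strata in |
|---|---|---|---|---|---|---|
| 0 | 0.314 | 0.315 | 1.00 | 5% | 0.315 | 0.316 |
| 0.1 | 0.314 | 0.302 | 1.04 | 4% | 0.299 | 0.301 |
| 0.2 | 0.315 | 0.287 | 1.10 | 3% | 0.282 | 0.284 |
| 0.3 | 0.316 | 0.269 | 1.17 | 2% | 0.264 | 0.265 |

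With the strata in the model, type I error returns to about 5%. The true SE hardly moves (0.269 against 0.265 even at R² = 0.3), because the allocation already supplies the balance. Prognostic strata with an unequal centre split were not examined.

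**Step 2: baseline.** For the 6-month effect, with three visits, equal correlation ρ between them and known covariance:
- Baseline unused: SE = √(2/20) = 0.316.
- Baseline as a covariate (ANCOVA): SE = √[(2/20)(1 − ρ²)].
- Baseline as a response with one mean for both arms: the same SE as ANCOVA.
- Baseline means free by arm, change contrasted: SE = √[(2/20) × 2(1 − ρ)].

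| ρ | Unused | ANCOVA or common mean | Change contrast | Unused / ANCOVA | Change / ANCOVA |
|---|---|---|---|---|---|
| 0.3 | 0.316 | 0.302 | 0.374 | 1.05 | 1.24 |
| 0.5 | 0.316 | 0.274 | 0.316 | 1.15 | 1.15 |
| 0.7 | 0.316 | 0.226 | 0.245 | 1.40 | 1.08 |

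**Step 3: the two parts overlap.** Where baseline carries the same strata effect (R² = 0.2, ρ = 0.5), the reported SE is 0.282 with strata alone and 0.265 with strata and baseline. The gains in steps 1 and 2 should therefore not be added.

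**The case against.** A reader might infer that the plan excludes the strata and the baseline score, and so gives wrong standard errors and lost precision. The documents do not support that, for four reasons.

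- **The list is open.** The covariates are introduced as examples, so nothing excludes disease activity or centre. A statistical analysis plan that is not shown may complete the list. This stands, and it limits the point to factors not named. It does not remove the mismatch: the protocol chose to give examples, and they do not follow its own design.
- **Baseline may already be used.** In a repeated-measures mixed model, baseline can be the first response and would then not appear as a covariate. With a common baseline mean nothing is lost. This also stands, but the text does not choose that form, and the version with baseline means free by arm does lose precision.
- **The standard-error fault is conditional and conservative.** It needs prognostic strata, for which the protocol gives no figure. It makes intervals too wide rather than too narrow, and true precision is nearly unchanged. This stands in full.
- **Harm to the later trial is uncertain.** That trial's model is not specified, and it will include further centres, so centre effects from two sites may not carry over. Any error would point to a larger sample, so an underpowered later trial does not follow.

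The effect estimates are also secondary. The feasibility rates and acceptability do not depend on this model.

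**Conclusion.** The point holds as a mismatch and an unsettled choice. The stratification factors are not among the named covariates, and the handling of baseline is not stated. The text itself is certain; the size rests on assumed values.

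- **Strata, if prognostic and left out:** reported standard errors about 4% to 10% too large and residual variance inflated by 11% to 25%, at an assumed R² of 0.1 to 0.2. True precision hardly changes.
- **Baseline, at an assumed correlation of 0.5 to 0.7:** the standard error is about 15% to 40% larger than ANCOVA if baseline is unused, and about 15% to 8% larger if baseline means are free by arm and change is contrasted. There is no loss with a common baseline mean.

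Severity is modest, because only secondary estimates and the variance for the later trial are affected. The correction is worth making because that variance is a stated purpose of the pilot and the data are already to be collected.

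**What to change.** In the Statistical Plan, replace the covariate sentence with a statement that the mixed model for every mentee outcome:

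- includes disease-activity stratum and study centre as main effects (with about 10 parents per stratum, or fewer if disease activity has more than two levels, separate stratum-by-stratum terms are not practical);
- uses the baseline score either as a covariate or as a repeated response whose mean is constrained equal across arms;
- may also include the child's age and sex;
- does not include the number of mentoring sessions in the treatment-effect model. Sessions accrue after randomisation, and only in the experimental arm during follow-up, since the waitlist is offered the program after all outcome measures are complete. Adjusting for them distorts the treatment effect.

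Take the variance estimate for the later trial from this same model.

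The cost is a sentence or two and no new data. With two disease-activity levels and baseline as a covariate, it uses 1 + 1 + 1 = 3 degrees of freedom out of 40. More disease-activity levels would use more, and the protocol does not state how many there are. If the strata turn out not to be prognostic, adding them costs almost nothing (reported SE 0.315 against 0.314).

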Experimental Group. In addition to standard medical care provided to their child, parents in the experimental group will receive online peer mentoring via the iParent2Parent Program. The iParent2Parent program is a tailored peer-mentorship program that provides modeling and reinforcement by peers (trained parents of children with JIA) to parents of children diagnosed with JIA. The program will run over 2-3 months via 5-10 weekly to bi-weekly Skype calls. [name] will identify 5-7 suitable mentors (male and female) per site who meet eligibility criteria. A member of the research team will interview interested mentors, describe the program, outline requirements, and answer any study-related questions. During mentor training, all mentors will meet with [name], a licensed psychologist, who will screen for potential psychosocial concerns and considerations when taking on the role of a mentor (e.g., the personal impact of discussing their own child's JIA, speaking with other parents who have a child with JIA). Efforts will be made to pair mentors and mentees who share similar characteristics (e.g., sex/gender) as well as their child's characteristics (e.g., age, diagnosis). During the study period, mentors may be assigned up to 3 mentees at any time. The total number of mentees a peer mentor takes on is their choice. Mentees may be from either SickKids or IWK Health Centre. Before assigning a mentee, the research coordinator will reach out to the peer mentor to discuss additional commitment and assign mentees based on availability and willingness of mentors. A research assistant (RA) at each participating site will facilitate initial Skype calls. Dyads will be responsible for scheduling remaining calls at mutually agreeable times (same time each week with flexibility to schedules). Mentors and mentees may coordinate future calls via Skype or email. If participants cannot complete the iPeer2Peer intervention via Skype (e.g., no access to computer and/or internet), a phone option will be made available for participants to take part in the program.

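### The between-arm model adjusts for number of mentoring sessions, a post-randomisation part of the treatment that is zero in every control; depending on the model form this can distort the secondary effect estimates

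*Protocol*

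**What the plan says.** In the protocol's Statistical Plan, provided parametric assumptions are met, "linear mixed models will be used to test intervention effects on all outcomes". The next sentence reads "We will adjust for important factors such as child age, sex, and number of mentoring sessions in our model". Nothing confines the session count to a separate dose-response analysis, to the programme arm, or to the mentors' outcomes.

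The secondary outcome that this model serves is "determination of treatment effect estimates for mentee participants" (Outcomes Measures). Research Question II sets programme parents against the waitlist, and Specific Aims passes the resulting effect sizes to the sample size of a later multisite trial.

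Three other places fix what the session count looks like in each arm:

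- Experimental Group: "The program will run over 2-3 months via 5-10 weekly to bi-weekly Skype calls".
- Control Group: "The control group will be on a waitlist and receive usual care without intervention", and "The iParent2Parent Program will be offered after completion of all outcome measures".
- The visit schedule, under Both Groups, is the same in each arm: "Primary and secondary outcome measures will be collected online from both groups at baseline, 3 months, and 6 months".

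Study Design has parents "randomized to the experimental (iParent2Parent Program) (n=20) or control (waitlist) (n=20) group".

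**The concern.** A covariate in a randomised comparison should be fixed before randomisation. The session count is not: it accrues during the programme, and it is the programme. Every control has a count of zero at all three visits by design, so controls carry no information on the slope for sessions. That slope comes only from the 20 or so programme parents. Their attendance is partly self-selected, because dyads arrange their own calls and the Limitations section deliberately leaves the number of calls flexible.

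At stake is the effect size that answers Research Question II and feeds the design of the next trial. A coefficient pulled towards zero, or moved by who chooses to attend, could misdirect that design. The covariate could also be carried forward into the larger trial's model.

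**Working it through.** The plan gives no effect size, SD or power calculation for this model, so there is no planned figure to reproduce. The total of 40 rests on a pilot-study rule and enters here only as n = 20 per arm.

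**Inputs from the protocol.** n = 20 per arm; sessions S = 0 in controls; 5-10 calls planned in the programme arm.

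**Assumptions.** Outcome SD of 1; true programme effect of 0.50 SD; S uniform on whole numbers in the programme arm, either 5-10 (the plan) or 0-10 (allowing for non-adherence). Mean m and variance v of S are then 7.5 and 35/12 = 2.92, or 5 and 10.

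**Form A: arm main effect on follow-up scores.** Fit Y = a + b·G + c·S + error, with G the arm. Because S = 0 in all controls, c is the within-programme slope and

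b = D − c·m,

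where D is the plain difference in means. So b is the arm contrast carried back to zero sessions. With D = 0.50:

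| Situation | c·m | b, by formula | b, simulated (5-10 / 0-10) |
|---|---|---|---|
| Benefit proportional to sessions | 0.50 | 0.00 | 0.01 / 0.00 |
| Half the benefit dose-dependent | 0.25 | 0.25 | 0.27 / 0.25 |
| Benefit unrelated to sessions | 0 | 0.50 | 0.49 / 0.50 |

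The simulations used 20,000 replicates. Without sessions in the model, the arm coefficient averaged 0.50 throughout.

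*Attendance related to prognosis.* Take a within-arm correlation r = 0.25 that arises from a shared cause. Then c = r/√v and b shifts by −r·m/√v:

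- 5-10: −0.25 × 7.5/1.708 = −1.10 SD.
- 0-10: −0.25 × 5/3.162 = −0.40 SD.

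The sign reverses if parents with worse outcomes attend more. At an assumed 0.15 SD per session, b rises by 0.15 × 7.5 = 1.13 to 1.63 (5-10), or by 0.15 × 5 = 0.75 to 1.25 (0-10).

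*Precision.* The variance inflation factor for arm is 1 + m²/(2v), and the unadjusted SE is √(2/20) = 0.32.

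- 5-10: 1 + 56.25/5.83 = 10.6, so SE = √(0.1 × 10.6) = 1.03. Simulated SE is 1.08, a ratio of 1.08/0.32 = 3.4.
- 0-10: 1 + 25/20 = 2.25, so SE = √(0.1 × 2.25) = 0.47. Simulated SE is 0.49, a ratio of 0.49/0.32 = 1.5.

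The simulated SEs are slightly larger because the variance of S differs from sample to sample.

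**Form B: three visits, group-by-time effect, sessions as a subject-level main effect.** Such a term adds the same amount at baseline, 3 and 6 months, so it cancels from every change from baseline. In a simulation with a random intercept, complete data and benefit proportional to sessions, the group-by-3-month coefficient was the same with and without sessions, to rounding error: 0.518 both ways for 5-10 and 0.489 both ways for 0-10.

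**Form C: three visits, sessions as a post-baseline (time-varying) term.** The cancellation is lost. In the same simulation with 5-10 sessions the coefficient averaged −0.02, with SE 0.73.

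**Outcome variance.** In the single-outcome runs, residual variance was 0.99 without sessions and 0.96 with them. Collinearity widens the SE of the arm coefficient; it barely moves the SD used for sample size.

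**The case against.** The strongest reply is that the planned analysis is a repeated-measures mixed model, and a single-outcome regression is not that model. If the intervention effect is the group-by-time term and sessions enters as child age does, the effect estimate does not move (Form B). The protocol does not say which form is meant, and that detail may sit in a statistical analysis plan that is not at hand. This stands. It makes the harm conditional, but it supplies no reason for keeping the covariate: under Form B sessions does nothing for the effect estimate, and under Forms A and C it damages it.

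A reader might infer that the model removes the programme effect outright, with a standard error several times too large. The documents do not support that as a general statement. Removal needs Form A or C together with benefit proportional to sessions; where benefit is unrelated to sessions, the coefficient is unbiased and only imprecise. The 3.4-fold SE needs every programme parent to complete at least five calls. Outcomes Measures sets attrition below 15% and adherence above 80% as acceptable, so some parents may complete fewer; at 0-10 sessions the factor is 1.5.

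A reader might also infer that the variance passed to the next trial is spoiled. It is not: residual variance barely changes, and the Statistical Plan states the estimation of variance and correlation in a separate sentence before the adjusted model.

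Two smaller points are fair. The covariate list is illustrative, although it names sessions expressly. The sentence also covers mentor outcomes, where there is no randomised comparison and a session count raises no such problem.

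**Conclusion.** The concern holds in a limited form. As written, the protocol puts a post-randomisation component of treatment, structurally zero in one arm, into the model meant to estimate the effect of that treatment. An analysis plan that follows the sentence would inherit the flaw.

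Its consequence depends on a model form that the protocol leaves open: anything from no change in the effect estimate to a coefficient that no longer answers Research Question II. The numerical sizes rest on the assumed 0.50 SD effect, unit SD, uniform session counts and the assumed attendance-prognosis association. The structural result, b = D − c·m in the main-effect form, does not depend on those values.

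The damage is confined to the secondary effect-size estimates. The primary feasibility rates with their confidence intervals do not use this model.

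**What to change.** In the Statistical Plan, delete the session count from the covariates of the between-arm model and state that this model adjusts only for variables fixed before randomisation. If a relation between sessions and outcome is of interest, report it separately within the programme arm, labelled exploratory and non-randomised. The session count may stay as a descriptor in the mentor analysis.

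The cost is an edit to one sentence, with no extra data and no extra participants.
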